3152-201-002 Rollover Phase 2	Open-label Rollover Study of Cenicriviroc for the Treatment of Liver Fibrosis in Adult Subjects with Nonalcoholic Steatohepatitis (NASH)	167 Adult participants with NASH enrolled in the study who completed both Treatment Period 1 and Treatment Period 2 in the CENTAUR study, or who completed the AURORA study because of progression to cirrhosis or reaching an adjudicated liver-related clinical outcome in either Part 1 or Part 2 of the study; all 167 received CVC	Cenicriviroc mesylate 150 mg immediate release oral tablet daily for duration of trial	The CVC drug product was formulated with fumaric acid (160 mg) and other excipients, including microcrystalline cellulose, croscarmellose sodium, colloidal silicon dioxide, magnesium stearate, and Opadry® II yellow (film coating). The CVC drug product was provided as 150-mg yellow-coated, immediate release tablets for oral administration.	Safety; incidence of adverse events
Noteworthy findings: CVC 150 mg once daily was well tolerated in this study. No clinically significant safety findings were identified. The study was terminated early for administrative reasons					

Study Number/Phase	Study Title	Participant Description	Dose & Administration	CVC Formulation	Endpoints
3152-301-002 Phase 3	AURORA: A Phase 3, Multicenter, Randomized, Double-Blind, Placebo-Controlled Study to Evaluate the Efficacy and Safety of Cenicriviroc for the Treatment of Liver Fibrosis in Adult Subjects with Nonalcoholic Steatohepatitis	
Part 1: A total of 1288 participants with NASH were analyzed in Part 1 (859 participants in Arm A; and 429 participants in Arm B) [1293 participants were randomized (861 to the CVC group and 432 to the placebo group)]
 
Part 2: A total of 1769 participants with NASH were analyzed in the full study cohort (1180 participants in Arm A, and 589 participants in Arm B) [A total of 1778 participants were enrolled in the full study cohort. Of these, 1185 participants were randomized to the CVC group and 593 participants were randomized to the placebo group.]
	Cenicriviroc mesylate 150 mg immediate release oral tablet (Arm A) or placebo (Arm B) once daily (2:1)	Cenicriviroc mesylate 150 mg immediate release oral tablet (Arm A) or placebo (Arm B) once daily (2:1)	
Part 1: Proportion of participants with improvement in fibrosis by at least 1 stage (NASH CRN system) AND no worsening of steatohepatitis (no worsening of lobular inflammation or hepatocellular ballooning grade) Safety and tolerability
 
Part 2: Composite endpoint of histopathologic progression to cirrhosis (defined by NASH CRN Fibrosis Stage 4), liver-related clinical outcomes, and all-cause mortality, as measured by the time to first occurrence of any of the listed adjudicated events (clinical outcomes composite endpoint) Safety and tolerability

Study Number/Phase	Study Title	Participant Description	Dose & Administration	CVC Formulation	Endpoints

Noteworthy findings: The primary endpoint was not met for Part 1, leading to early termination of the study. No meaningful numerical or statistical difference was observed between CVC 150 mg once daily and placebo with respect to the key efficacy endpoints regarding liver histology at Month 12 relative to the screening biopsy in adult participants with a liver biopsy diagnosis of NASH and Stage 2 or 3 liver fibrosis (by NASH CRN system). CVC 150 mg once daily was, in general, well tolerated in this study, and there were no treatment-related AEs that were fatal or life-threatening.
					
CLJC242A2201J Phase 2	TANDEM: A randomized, double-blind multicenter study to assess the safety, tolerability, and efficacy of CVC with tropifexor in adults with NASH and LF	40 healthy participants (20 in Group 1 and 20 in Group 2)	193 adults with NSH and LF	150mg tablets immediate release	Occurrence of AEs, SAEs and AESIs. AEs resulting in d/c. Effect on vital signs over 48w. Proportion of patients with at least 1 point improvement in fibrosis and proportion with resolution of steatohepatitis

Noteworthy findings: Neither of the combination therapies, tropifexor 140 mcg + CVC 150 mg or tropifexor 90 mcg + CVC 150 mg, increased the likelihood of response compared with either tropifexor 140 mcg alone or CVC 150 mg alone. The safety profiles of the combination therapies of tropifexor 140 mcg + CVC 150 mg and tropifexor 90 mcg + CVC 150 mg were similar to those of each monotherapy, with no additional emergent safety signals compared to those identified and reported in previous monotherapy studies. Overall, pruritus, nausea, and fatigue were the most frequently experienced AEs. The proportion of participants who experienced pruritus was highest in the tropifexor 140 mcg alone group and notably lower with tropifexor 140 mcg + CVC 150 mg combination treatment. Similar patterns are noted for fatigue and urinary tract infection, and this pattern may be explained by the DDI by which CVC treatment reduces tropifexor levels. No deaths were reported in the study. Most SAEs were single occurrences. There were few AESI of liver injury. Elevations in ALT and AST were higher in the tropifexor-containing groups, with most elevations transient and reversible. There was no drug-induced serious hepatotoxicity detected, and no participant met Hy's law criteria (total bilirubin $>2 \times$ ULN and ALT $\geq 3 \times$ ULN) at any time after start of study treatment.
					

Study Number/Phase	Study Title	Participant Description	Dose & Administration	CVC Formulation	Endpoints
CLJC242A2101 Phase 1	A randomized, parallel group, 3-arm, double-blind, double-dummy study to investigate the drug-drug interaction potential between tropifexor (LJN452) and cenicriviroc (CVC) in healthy and healthy but overweight to obese subjects	42 healthy and healthy but overweight to obese participants with BMI of up to 32 kg/m ²	Arm 1: 60 µg tropifexor + CVC placebo daily (n=14) Arm 2: 150 mg CVC + tropifexor placebo daily (n=14) Arm 3: 60 µg tropifexor + 150 mg CVC daily (n=14)	CVC is available as 150 mg yellow-coated immediate-release tablets for oral admin.	PK of tropifexor, CVC, and their metabolites Safety assessments and measurements (including physical examination, vital signs, ECG, clinical laboratory evaluations and AEs) up to and including the end of study visit

Noteworthy findings: When tropifexor is used in combination with CVC, an increase in the dose of tropifexor may be considered to compensate for the lower exposure seen when co-administered with CVC. Overall, administration of tropifexor alone, CVC alone, and tropifexor + CVC was considered to be well tolerated by the participants in the study. Co-administration of tropifexor and CVC did not increase the safety and tolerability profiles when compared to administration of each drug independently. All reported TEAEs were of mild severity. There were no deaths reported during this study, and 1 SAE (unrelated ovarian torsion) was reported after the clinical database cut-off date. One participant who received tropifexor + CVC discontinued from the study due to a TEAE (rash), which was suspected to be definitely related to the study drugs. No clinically significant changes were noted in laboratory parameters, vital signs, or ECG parameters.

1.1	Reviewed for Protocol version 2.0 with no changes needed.	Apr 15, 2024
2.0	
Section 2:
 
Removed details on Interim monitoringIn Section 2.3.1, clarified outcome measure description (most diseased vessel) and revised analysis approach to use linear regression instead of t-test.Added Section 2.3.3: exploratory analyses.Added Section 2.6: regarding timing of final analyses. 
Section 3:
 
Added Section 3.1: Key definitions section.Revised Section 3.1 for clarity, updated to Section 3.2.Revised Section 3.2 to include other outcome measures and to update presentation structure into table-list. Updated to Section 3.3 
Section 4.1:
 
Added Section 4.1.1 and 4.1.2: key dates and data inclusion/exclusion for data to be analyzed.Revised Section 4.1.3 (previously 4.1): updated Day 1, week 4, and week 22 definition/range. Updated baseline definitions for outcomes to be based on entry instead of pre-entry/entry.In Section 4.1.4 (previously 4.2.1): added complete-case set definition.Revised Section 4.2: cleaned up sentences and moved details to be in Section 5. 
Section 5:
 
Added protocol deviation table to be reported.Modified components of baseline characteristics summary.Updated summary measures for baseline characteristics, study status, and treatment status from continuous to categorical.Added analysis set to be used, groups, statistical tests, and other details relevant to each table to be generated.Added sections on all listed outcomes and associated details.	July 18, 2024

1 Introduction

1.1 Purpose

This Primary Statistical Analysis Plan (SAP) describes the primary, secondary, and other outcome measures that will address specific study objectives and interim monitoring of the A5415 study. The Primary SAP includes general analytic approaches for all primary, secondary, and other outcome measures that will be included in the primary manuscript(s), Conference on Retroviruses and Opportunistic Infections (CROI) submission, or submitted to ClinicalTrials.gov (regardless of the reporting timeline). The Primary SAP facilitates discussion of the statistical analysis components among the writing team and statisticians, helping them agree on the statistical analyses to be performed and presented in the final analysis report.

An Analysis Implementation Plan (AIP) will also be prepared to provide more detailed outlines of tables, figures, and coding descriptions.

1.2 Version History

Version 1.0: Original version based on Protocol Version 1.0 dated August 22, 2022.

Version 2.0: Prepared leading up to the final analysis.

- The study team revised baseline and week 24 testing for immunological outcomes from averaging pre-entry/entry and week 22/24 to only using entry and week 24 samples due to budget constraints.
- Other changes include updates to visit window definitions, adds more details and clarifications to analytic plans for the primary and secondary objectives, as well as providing analysis plans for exploratory objectives that will be included in the Primary Statistical Report. See Version History Table for more details.

2 Study Overview

2.1 Study Design

A5415 is a double-blind, randomized, placebo-controlled, phase II trial to evaluate 24 weeks of Cenicriviroc mesylate (CVC) to reduce arterial inflammation among individuals living with chronic HIV on ART with viral suppression. CVC or placebo for CVC will be administered for 24 weeks to participants. The target sample size was 93 participants (62 in the CVC arm and 31 in the placebo arm). The study enrolled between May 2023 and January 2024 with a final sample size of 110 participants.

2.2 Hypotheses

Cenicriviroc mesylate (CVC) will decrease vascular inflammation as measured by 18F-fluorodeoxyglucose (FDG)-positron emission tomography (PET)/computed tomography (CT) cardiac imaging.

2.3 Study Objectives

This Primary SAP addresses the following primary and secondary objectives listed in the study protocol as well as other study objectives in the protocol that will be analyzed for the primary statistical report.

2.3.1 Primary Objective and Estimand

See Section 3.1 for details about TBR-related terms.

Primary Objective 1: To assess whether CVC treatment results in reduced arterial inflammation by comparing the changes in arterial target-to-background ratio (TBR) in the carotid arteries and aorta after treatment with CVC versus placebo.	
Estimand description	Percentage change in the arterial 18-FDG-PET TBR in the most diseased segment (MDS) of the carotid arteries and aorta following 24 weeks of CVC therapy among virally suppressed people living with HIV with at least one cardiovascular risk factor.
Treatment	Addition of CVC to background ART compared to ART alone.
Target population	Analysis set
Individuals living with HIV who are ≥ 45 years old, have at least one cardiovascular risk factor, and are on stable NNRTI-based or unboosted INSTI-based ART regimen, with suppressed HIV-1 RNA for ≥ 48 weeks prior to CVC start and who remain on the same ART drug class over an additional 24 weeks of CVC.	Participants who remain on study treatment for at least 22 weeks, and remain on the same ART drug class during the study.
Variable(s)	Outcome measure(s)
Fold change in 18-FDG-PET TBR, measured in the MDS of the most diseased vessel between the left and right carotid arteries and aorta over 24 weeks of CVC treatment	Fold change from baseline to week 24 in 18-FDG-PET TBR of the MDS of the most diseased vessel between the left and right carotid arteries and aorta. MDS TBR will be \log_{10} transformed ($\log_{10}[\text{week 24}] - \log_{10}[\text{pre-entry}]$) for analysis and back transformed for a fold change interpretation.
Handling of intercurrent events	Handling of missing data
The following intercurrent events are relevant to the estimand: - Change in background ART regimen not within the same drug class: excluded (principal stratum) - Change in background ART regimen within the same drug class: ignored (treatment policy) - Treatment interruption or missed doses: ignored (treatment policy) - Permanent discontinuation of treatment or background ART: Excluded (principal stratum) - Death – excluded (principal stratum) - Prohibited medications – excluded (principal stratum) - Pregnancy or breast-feeding – excluded (principal stratum)	Missing data due to unreadable or missed scans will be handled by using multiple imputation. A sensitivity analysis for the primary analysis will include complete case analysis.
Population-level summary statistic	Analysis approach
Geometric mean fold change (expressed as a percentage) in arterial MDS TBR after 24 weeks of treatment with and without CVC.	Fold change in TBR (1 - the geometric mean change) will be summarized by treatment groups with a 95% confidence interval. The relative treatment difference will be described as a geometric mean difference (active compared to placebo) and compared with a linear regression, stratified by statin use.
A supplementary analysis to the primary analysis will include participants who remain on treatment for at least 12 weeks and remain on the same ART drug class. A second supplementary analysis will exclude participants with confirmed HIV-1 RNA > 200 copies/mL or ART interruption for 14 or more consecutive days at any time during the course of the study.	

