6.2.4 Discontinuation Evaluations

Evaluations for Randomized Participants Who Do Not Start Study Treatment

All eCRFs must be keyed for the period up to and including the Entry visit.

No follow-up evaluations are required for randomized participants who do not start the study treatment.

Premature Treatment Discontinuation Evaluations

The premature treatment discontinuation evaluations, as noted in [section 6.1](#), will be performed in the following situations:

- Combined premature treatment and study discontinuation
- Premature treatment discontinuation (see [section 9.1](#)) but continuing with study follow-up (i.e., on study/off study treatment).

Site personnel should notify the A5415 CMC via email CMC ([contact]) within 48 hours of learning of any participant who prematurely discontinues study treatment.

Stored samples must be drawn as soon as possible, preferably within 7 days after the last study treatment dose. All other evaluations must be performed as soon as possible, preferably within 14 days after the last study treatment dose.

The FDG-PET/CT imaging is not required if the participant prematurely discontinues study treatment before week 12. If premature treatment discontinuation is at or after week 12 and before week 24, the FDG-PET/CT imaging must be performed as soon as possible, preferably within 7 days after the last study treatment dose. The participant should be instructed to return to clinic in a fasting state. Refer to the A5415 MOPS for the pre-imaging dietary instructions and [section 6.3.5](#) for the fasting instructions. If premature treatment discontinuation is not due to pregnancy, refer to [section 6.3.5](#) for the pregnancy test guidelines and [section 6.3.9](#) for pregnancy testing prior to conducting the FDG-PET/CT imaging. A participant who is found to be pregnant at the premature treatment discontinuation visit will not have the FDG-PET/CT imaging performed.

A participant who prematurely discontinues study treatment because of pregnancy will NOT have the FDG-PET/CT imaging performed and is NOT required to fast prior to the discontinuation visit.

Participants should be encouraged to continue to attend all study visits and receive study evaluations as per [section 6.1](#), with the exception of the FDG-PET/CT imaging at week 24 and the PK evaluation. They will be followed on study/off study treatment through completion of the study.

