2.4 Overview of Sample Size Considerations

The target sample size is 75 participants (50 in the CVC arm and 25 in the placebo arm) with baseline and follow-up PET/CT. To allow for some loss to follow-up and participants unwilling or unable to complete 2 scans, the study planned to enroll 93 participants (62 in the CVC arm and 31 in the placebo arm). Final enrollment was 110 participants.

The primary analysis will focus on between-treatment arm differences in the within-participant changes in arterial MDS TBR (the measure of arterial inflammation by PET/CT). Based on a superiority trial design with two-sided $\alpha=0.05$, assuming a standard deviation (SD) of 0.065 \log_{10} TBR for change in MDS TBR, a total of 75 participants providing complete, evaluable data sets will ensure 80% power to detect a between-groups difference of 0.046 \log_{10} MDS TBR (which is a 10% reduction from baseline).

The assumptions underlying the power calculation are as follows:

- 1) The target effect size for the change in MDS TBR on therapy of 10% is based on the observation of a statin intensification study.
- 2) The assumed SD for change in (\log_{10}) MDS TBR of 0.065 is derived from the placebo arm of ACTG A5314.

3) The use of a two-sided, two-sample T-test with type-I error rate of 5%.

The assumption that 93 enrolled participants will provide 75 participants with evaluable data is derived by 20% total data loss due to drop-out after randomization (including premature discontinuation of study treatment and change in background ART drug class).

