4.1.3 Analysis Windows

Defined as follows:

- Day 1 = study treatment initiation date
- Week 4: -21 / +14 days
- Weeks 8, 12, 16: +/- 14 days
- Week 22: -14 / +7 days
- Week 24: -7 days up to maximum days observed

Baseline refers to study evaluation closest to Week 0 prior to initiation of study treatment unless otherwise stated.

In the event of multiple results within a study window, the result closest to the scheduled evaluation week based on the time since study treatment initiation date will be used. Exceptions may include repeat visits for confirmation of events such as virologic failures.

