4.1.4 Analysis Sets

Efficacy set (per-protocol set): All eligible participants who remain on study treatment for at least 22 weeks and remain on the same ART drug class during their entire study period.

Complete-case set: Efficacy set participants who have baseline-week 24 pair of PET/CT scan data.

Supplementary efficacy set one: All eligible participants in the efficacy set as well as participants who remained on study treatment for at least 12 weeks and remained on the same ART drug class during their entire study period.

Supplementary efficacy set two: All eligible participants in the efficacy set excluding participants with confirmed HIV-1 RNA > 200 copies/mL or ≥ 14 consecutive days of ART interruption at any time during the course of the study.

Safety set: All enrolled participants who initiate study treatment.

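### SAP 2.3.1 both excludes and includes participants who permanently stop treatment after week 22, and a discontinuation scan taken before about day 161 has no route to the week-24 value

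*SAP*

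**What the plan says.** **Who is analysed.** In the SAP 2.3.1 estimand table, the intercurrent-event cell lists "Permanent discontinuation of treatment or background ART: Excluded (principal stratum"). It sets no time limit. The Analysis set cell of the same table requires at least 22 weeks on study treatment and no change of ART class. SAP 4.1.4 repeats this for the efficacy set, which it defines as "All eligible participants who remain on study treatment for at least 22 weeks and remain on the same ART drug class during their entire study". Protocol 10.6.1 uses the same 22-week mark. The inclusion table shell in SAP 7.1 has a 22-week column and no column for discontinuation. SAP 4.1.2, which says it applies the 2.3.1 handling, lists never starting, ineligibility, prohibited medication, death and pregnancy. Permanent discontinuation is not on that list.

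**Which scan is used.** For a stop at or after week 12 and before week 24, protocol 6.2.4 says that "the FDG-PET/CT imaging must be performed as soon as possible, preferably within 7 days after the last study treatment dose". The same section then removes the later week-24 scan. SAP 4.1.3 gives the analysis window as "Week 24: -7 days up to maximum days observed" and the week-22 window as 14 days before to 7 days after. No SAP rule assigns a discontinuation scan to week 24. SAP 7.2 multiply imputes week-24 scans that were missed or cannot be read. The complete-case set in SAP 4.1.4 requires a baseline and week-24 pair.

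**Related analysis.** Protocol 10.6.3 plans a sensitivity analysis that uses evaluations at premature discontinuation after week 12, provided the participant was on treatment within 7 days of the evaluation. Its SAP counterpart, supplementary efficacy set one, keeps the 12-week criterion but says nothing about which scan is used.

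**The concern.** Two rules in one table give opposite answers for a participant who completes 22 weeks and then stops for good, for example on day 155 because of an adverse event. The table defines the primary estimand, so the conflict concerns who is in the primary analysis.

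If that participant is kept, the SAP has no place for the scan that the protocol requires. A scan done promptly on days 155–160 precedes the week-24 window. It falls in the week-22 window, for which there is no TBR endpoint. On a literal reading an observed value, taken within days of the last dose, would be replaced by an imputed one in the primary analysis and dropped from the complete-case sensitivity analysis.

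Accrual closed on January 5, 2024, and SAP version 2.0 is dated July 18, 2024, more than 24 weeks later. A rule left open at that point would be settled with follow-up essentially complete.

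**Working it through.** **1. The plan's own figure.** Inputs from SAP 2.4: "The use of a two-sided, two-sample T-test with type-I error rate of 5"%; "will ensure 80% power to detect a between-groups difference of 0.046" log10 TBR; SD of change in log10 "MDS TBR of 0.065 is derived from the placebo arm of ACTG A5314"; evaluable sample "75 participants (50 in the CVC arm and 25 in the placebo arm) with baseline and follow-up PET/CT".

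- Noncentrality = 0.046 / (0.065 × √(1/50 + 1/25)) = 0.046 / 0.01592 = 2.89, with 73 degrees of freedom.
- Power = 81.4%, or 80.9% with the exact 10% reduction, −log10(0.9) = 0.0458. The stated 80% is reproduced.

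**2. Day arithmetic.** Counting week k as day 7k from the start of treatment:

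- 22 weeks = 22 × 7 = day 154.
- Week 24 = 24 × 7 = day 168, so its window opens on 168 − 7 = day 161.
- The week-22 window is days 154 − 14 = 140 to 154 + 7 = 161. Day 161 lies in both windows and is counted here as inside week 24.

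**3. Membership conflict.** It covers any permanent stop from day 154 until the week-24 evaluations, except stops that SAP 4.1.2 removes anyway (prohibited medication, pregnancy, death).

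**4. Window gap, if the 22-week rule governs.** Cross each last-dose day from 154 to 167 with scan delays of 0 to 7 days. A scan misses the week-24 window when last-dose day + delay < 161.

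| Last dose (day) | Delays outside the window (days) | Count of 8 |
|---|---|---|
| 154 | 0–6 | 7 |
| 155 | 0–5 | 6 |
| 156 | 0–4 | 5 |
| 157 | 0–3 | 4 |
| 158 | 0–2 | 3 |
| 159 | 0–1 | 2 |
| 160 | 0 | 1 |
| 161–167 | none | 0 |

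Total outside: 7 + 6 + 5 + 4 + 3 + 2 + 1 = 28 of 14 × 8 = 112 combinations, or 25%. Within the first week alone it is 28 of 56, or 50%. Other day-numbering conventions, such as week 24 = day 169, give 19% to 32%. If every scan were on the day of the last dose, 7 of 14 stop days would be outside (6 to 8 across conventions).

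**5. How many people.** The documents give no count. As an illustration, assume that the plan's 20% data loss consists entirely of treatment stops, spread evenly over 24 weeks among the 110 enrolled:

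- Membership conflict (two weeks): 110 × 0.20 × 2/24 = 1.8.
- Stops in the first of those weeks: 110 × 0.20 × 1/24 = 0.9.
- Scanned before the window opens (half of the combinations): 0.9 × 0.5 ≈ 0.5.
- The last figure with the 15% loss that protocol 10.4 uses for non-imaging outcomes: 110 × 0.15 × 1/24 × 0.5 ≈ 0.3.

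Both percentages cover more than treatment stops (ART class change, for example), so these figures lean high on that account. A range of 0 to 2 is reasonable.

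**6. Effect on power.** Removing participants from the planned 75 in about a 2:1 ratio, with the formula in step 1:

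| Removed | Arms | Power |
|---|---|---|
| 0 | 50 + 25 | 81.4% |
| 1 | 49 + 25 | 81.1% |
| 3 | 48 + 24 | 79.7% |
| 6 | 46 + 23 | 78.0% |

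With 110 enrolled and 20% loss, 110 × 0.80 = 88 would be evaluable, so the trial also has some reserve over the planned 75.

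**The case against.** The strongest reply is that 22 weeks is the working definition of having completed treatment. The 2.3.1 table pairs each estimand concept with the way it is put into practice, and the practical cell says 22 weeks. SAP 4.1.4, the 7.1 shell and protocol 10.6.1 agree, and the absence of discontinuation from SAP 4.1.2 fits a rule that already covers it. This largely stands: the 22-week reading is clearly dominant. The SAP does not say so, however, and the untimed exclusion remains in the table that defines the estimand.

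A second reply is that imputation is inferred. SAP 7.2 imputes missed or unreadable scans and leaves the details to the Analysis Implementation Plan, which is not among the documents. A discontinuation scan that was done is arguably neither missed nor unreadable, and protocol 10.6.3 shows an intention to use such scans. This stands as a caution. Nevertheless, no written SAP rule brings a scan from before day 161 into the week-24 value, so the literal result is imputation.

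Three stronger readings are tempting, and the documents do not support them:

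- A reader might infer that every prompt scan after a stop between weeks 22 and 24 is lost. Scans after stops on days 161–167 are inside the window.
- A reader might infer that the plan discards the better scan and keeps the worse one. After a stop on day 155, a scan on day 161 is 6 days from the last dose, still within the protocol's preferred 7 days and closer to nominal week 24. Nothing in the documents shows that it is worse.
- A reader might infer a biased treatment estimate because late stopping differs by arm. It could differ, and the placebo arm is only about 110/3 ≈ 37, but the documents give no stopping rate by arm.

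**Conclusion.** The contradiction is real, and it sits inside the primary estimand table: one cell excludes the late stopper and the cell that defines the analysis set includes the same person. If the 22-week rule governs, there is a second, narrower defect. A stop on about days 154–160 followed by a scan before about day 161 leaves an observed value with no route into the endpoint, while stops on days 161–167 are handled properly.

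The size is small. On the assumptions shown (20% loss taken as all stopping, spread evenly), about 1.8 participants meet the membership conflict and about 0.5 the window gap. One lost participant costs about 0.3 points of power. This is a problem of definition, not of power. It is worth correcting because it decides membership of the primary set and because two sentences repair it.

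**What to change.** - In SAP 2.3.1, replace the intercurrent-event line with: *Permanent discontinuation of study treatment before 22 weeks, or permanent discontinuation of background ART at any time: excluded.* This matches SAP 4.1.4 and protocol 10.6.1. The background-ART clause has to stay, because shortening the line to treatment alone would open a new gap.
- In SAP 4.1.3, add: *For efficacy-set participants who stop study treatment at or after 22 weeks, the discontinuation scan taken within 7 days of the last dose is the week-24 value and is not imputed.* The complete-case set then includes these participants.
- Apply the same mapping to supplementary efficacy set one for stops after week 12, as protocol 10.6.3 intends.

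The cost is a few sentences in the SAP, with no new assessments and no change to conduct. The downside is that a few endpoint scans come earlier than nominal week 24: by up to about 2 weeks in the primary set, and by more in the supplementary set. The change should be made before any analysis by treatment arm. If that point has passed, record the choice and report the primary result under both readings.
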